5.3 Safety Endpoints

Safety endpoints will include:

- adverse events recorded during the study
- clinical laboratory measurements at Visit 1 (Day 0), Visit 4 (Day 90) , Visit 5 (Day 120) and Early Termination
- vitals sign measurements at Visit 1 (Day 0), Visit 4 (Day 90), Visit 5 (Day 120) and Early Termination
- physical examination at Visit 1 (Day 0), Visit 4 (Day 90), Visit 5 (Day 120), and Early Termination

5.4 Exploratory Endpoints

Exploratory endpoints will include:

- change in satisfaction for each TSQM domain from Visit 1 (Day 0) to Visit 5 (Day 120) for non-naïve ALL patients
- change in satisfaction for each TSQM domain from Visit 2 (Day 30) to Visit 5 (Day 120) for naïve ALL patients

6.0 ANALYSIS POPULATION AND ANALYSIS SUBSETS

6.1 All Participants Population

The All Participants population includes all patients who signed the informed consent form and were entered into the MY-T study web-based application. Study enrollment and patient disposition will be reported using the All Participants population.

6.2 BID Intent-to-Treat (ITT) Population

The BID ITT population includes all patients who received at least one dose of study drug, are part of the BID treatment group and have a valid post-dose efficacy measurement at Visit 2 (Day 30) or Visit 3 (Day 60) or Visit 4 (Day 90). Data will be analysed using the BID ITT population as per the Table Mock-Up (TMU) document.

6.3 TID Intent-to-Treat (ITT) Population

The TID ITT population includes all patients who received at least one dose of study drug, are part of the TID treatment group and have a valid post-dose efficacy measurement at Visit 2 (Day 30) or Visit 3 (Day 60) or Visit 4 (Day 90) or Visit 5 (Day 120). Data will be analysed using the TID ITT population as per the Table Mock-Up (TMU) document.

6.4 Intent-to-Treat (ITT) Population

The ITT population includes all patients who are included in either the BID ITT or TID ITT population. Data will be analysed using the ITT population as per the Table Mock-Up (TMU) document.

6.5 Safety Population

The Safety population includes all patients who received at least one dose of the study drug. All safety data including adverse events, physical examination parameters, vital signs, total testosterone and laboratory data will be analysed using the Safety population.

6.6 BID Per-Protocol (PP) Population

The BID PP population includes all BID ITT patients who completed the 90-day (Visit 4) Treatment Period without any major protocol deviations. Data will be analysed using the BID PP population as per the Table Mock-Up (TMU) document.

6.7 TID Per-Protocol (PP) Population

The TID PP population includes all TID ITT patients who completed the 120-day (Visit 5) Treatment Period without any major protocol deviations. Data will be analysed using the TID PP population as per the Table Mock-Up (TMU) document.

6.8 Per-Protocol (PP) Population

The PP population includes all patients who are included in either the BID PP or TID PP population. Data will be analysed using the PP population as per the Table Mock-Up (TMU) document.

7.0 DATA CONVENTIONS

7.1 Definitions

Visit 1 (Day 0) is defined as the day in which the patient provides informed consent and starts the study. All study days are determined relative to Visit 1 (Day 0).

End of treatment is defined as the day on which the last dose of treatment is taken. This date was not collected for this study.

End of study is defined as the last day on which data were collected from the patient. Using the Early Termination Visit eCRF, it is the date of early termination. Using the Visit 6 - Post Study Follow-Up (Day 150) eCRF, it is the post study follow-up date. Otherwise, it is the date of last contact, if the patient was lost to follow-up, or the date of death, if the patient died.

Baseline serum testosterone values will be defined as those values recorded on Visit 1 (Day 0). Naive patients were asked for 2 measurements (average used in analysis) and non-naive patients were asked for 1 measurement at Baseline (Visit 1/Day 0).

Serum Testosterone will be reported in (nmol/L). If value is reported in (ng/dL) then value will be multiplied by 0.0347 to convert to (nmol/L).

Testosterone collected in (pmol/L) will be considered Free Testosterone and will not be used in any analyses.

Hematocrit will be reported in (%). Values will be multiplied by 1 and if the value is less than 1 then the value will be multiplied by 100.

Total Cholesterol will be reported in (mmol/L). If value is reported in (mg/dL) then value will be divided by 38.67 to convert to (mmol/L).

LDL will be reported in (mmol/L). If value is reported in (mg/dL) then value will be divided by 38.67 to convert to (mmol/L).

HDL will be reported in (mmol/L). If value is reported in (mg/dL) then value will be divided by 38.67 to convert to (mmol/L).

Triglycerides will be reported in (mmol/L). If value is reported in (mg/dL) then value will be divided by 88.57 to convert to (mmol/L).

Hemoglobin will be reported in (g/L). If value is reported in (g/dL) then value will be divided by 0.1 to convert to (g/L).

ALT and AST will be reported in (U/L).

Study duration (days) will be defined as the (end of study date – date of informed consent + 1).

The ALL treatment group will be defined as patients who were either naïve or non-naïve.

The BID treatment group will be defined as patients who were either naïve or non-naïve and did not titrate to TID (Visit 5/Day 120).

The TID treatment group will be defined as patients who were either naïve or non-naïve and did titrate up to TID (Visit 5/Day 120).

7.2 Visit Windows

The visit window for all post baseline visits was a ± 3 day window relative to the expected nominal time point except for Early Termination visit. For example, Visit 2 is Day 30 ± 3 . For the purpose of the statistical analyses data entered at the nominal time points will be used (Visit 1/Day 0, Visit 2/Day 30, Visit 3/Day 60, Visit 4/Day 90, Visit 5/Day 120, Visit 6/Day 150 and Early Termination).

7.3 Missing Data

Dates with missing day will be imputed as the 15th. Dates with both missing day and month will be imputed as July 1st. Date of hypogonadism diagnosis will be imputed.

Missing TSQM domain scores for both the BID and TID treatment groups will be imputed using LOCF (Last Observation Carried Forward). For LOCF to apply there must be at least a Visit 2 domain score available so that the patient had sufficient exposure to give a measurable change. The TSQM domain scores will be calculated based on the LOCF domain. Summaries for paired change from Visit 1/Day 0 will require both TSQM domain scores at Visit 1/Day 0 and Visit 2/Day 30 to be available to be included in output. Summaries for paired change from Visit 2/Day 30 will require the TSQM domain scores at Visit 2/Day 30 to be available to be included in output.

Missing qADAM questions for both the BID and TID treatment groups will be imputed using LOCF (Last Observation Carried Forward). For LOCF to apply there must be at least a Visit 2 question available so that the patient had sufficient exposure to give a measurable change. The total qADAM score will be calculated based on the LOCF items. Summaries for paired change

from Visit 1/Day 0 will require both total qADAM scores at Visit 1/Day 0 and Visit 2/Day 30 to be available to be included in output.

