10.1 Adverse Events

Adverse event data will be tabulated separately for each treatment group (ALL, BID, TID) by system organ class and preferred term. Adverse events will be summarized by presenting counts and percentage of patients (each patient contributes a single count to a category) and the total number of events in each system organ class and in each system organ class/preferred term.

In addition, adverse event data with a possible drug relationship (possible, probable, definitely related) will be tabulated separately for each treatment group (ALL, BID, TID) by system organ class and preferred term. Adverse events will be summarized in a similar manner as above.

As well, adverse event data will be tabulated separately for each treatment group (ALL, BID, TID) by system organ class, preferred term and severity (mild, moderate, severe). Adverse events will be summarized by presenting counts and percentage of patients (each patient contributes a single count to a category) and the total number of events in each system organ class by severity and in each system organ class/preferred term by severity.

The Medical Dictionary for Regulatory Activities (MedDRA™ version 20.1) will be utilized for the coding of adverse events.

All adverse events that occurred on or after the date of informed consent up to 30 days after the end of study date will be summarized.

Serious adverse events will not be tabulated due to the expected small number of events. Narratives will be provided for serious adverse events.

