11.2 Disease Characteristics

Quantitative and/or categorical summaries will be presented for hypogonadal treatment status, baseline testosterone, and age of hypogonadism diagnosis by overall, naïve and non-naïve patients.

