11.5 Concomitant Medications

Concomitant medications will be recorded at Day 0 (Visit 1) and reviewed at each subsequent visit until the end of study. All medications taken 30 days prior to Day 0 (Visit 1) and during the study period will be tabulated. Numbers and percentages of overall, naïve and non-naïve patients will be presented for concomitant medication data levels 3 and 5. Medication will be coded using the Anatomical-Therapeutic-Chemical (ATC) classification text from the WHO Drug Dictionary version January 2017.

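### The SAP's 15th / 1 July date rule is worded for all dates with no floor at consent; if applied to adverse-event onset, it would drop some on-study events from the safety tables

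*SAP*

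**What the plan says.** Section 7.3 (Missing Data) opens with a rule on partial dates: "Dates with missing day will be imputed as the 15th. Dates with both missing day and month will be imputed as July 1st". The sentence after it reads "Date of hypogonadism diagnosis will be imputed". No other date field is named, and no lower or upper limit is put on an imputed date. The diagnosis date is used in Section 11.2, in the summaries of "hypogonadal treatment status, baseline testosterone, and age of hypogonadism diagnosis by overall, naïve and non-naïve patients".

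Two other sections select records by date:

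- Section 10.1 (Adverse Events) summarizes "All adverse events that occurred on or after the date of informed consent up to 30 days after the end of study date".
- Section 11.5 (Concomitant Medications) states: "All medications taken 30 days prior to Day 0 (Visit 1) and during the study period will be tabulated".

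Neither has a partial-date rule of its own. Section 7.1 fixes the ends of the adverse-event window. For the start, "Visit 1 (Day 0) is defined as the day in which the patient provides informed consent and starts the study". For the end, "End of study is defined as the last day on which data were collected from the patient".

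**The concern.** The 15th / 1 July convention suits a diagnosis made long before the study, where a shift of weeks or months hardly changes age at diagnosis. It suits badly a date that decides whether a record is counted. The rule is written for dates in general and is the only partial-date rule in the SAP, so a programmer building the adverse-event tables could reasonably use it for onset. A true on-study event could then be given a date before consent, or a date after the window closes, and be left out.

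For day-missing events the loss would fall in the consent month, just after the drug is started. Safety monitoring is a stated secondary objective (Section 2.2) and the study plans about 100 participants (Section 4.0), so a few lost events could alter a preferred-term row. Likewise, a medication stopped inside the 30-day look-back could be moved out of the table.

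**Working it through.** The SAP gives no figure on this point, so there is none to reproduce. The check enumerates calendar dates.

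**Inputs from the SAP:** the imputation rule (Section 7.3); the window from consent to end of study + 30 days (Section 10.1); Day 0 as the consent day (Section 7.1); follow-up at Day 150 (Section 3.0), so the window runs to Day 150 + 30 = Day 180 for a completer.

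**Assumptions:** consent spread evenly over a 365-day year; onset uniform over the stated days. The share of partly dated events is not given, so every percentage is conditional on an event being partly dated.

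**1. Day missing, moved before consent.** This happens only if onset is in the consent month and consent is on the 16th or later. Example: consent 20 March, onset 25 March, imputed 15 March, dropped. For consent on day k of an m-day month, the affected onset days number m − k + 1. Summing over k = 16 to m:

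- 31-day month: 16 + 15 + … + 1 = 136
- 30-day month: 15 + … + 1 = 120
- 28-day month: 13 + … + 1 = 91

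Over the year: 7 × 136 + 4 × 120 + 91 = 1,523 consent/onset pairs.

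| Onset range | All pairs | Moved before consent |
|---|---|---|
| Consent month only | 7 × 496 + 4 × 465 + 406 = 5,738 | 26.5% |
| Days 0-30 | 365 × 31 = 11,315 | 13.5% |
| Days 0-90 | 365 × 91 = 33,215 | 4.6% |
| Days 0-120 | 365 × 121 = 44,165 | 3.4% |
| Days 0-150 | 365 × 151 = 55,115 | 2.8% |

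**2. Day missing, moved past the window.** The 15th is at most 14 days after the true onset (onset on the 1st). An onset on or before end of study is therefore imputed no later than end of study + 14 days, inside the 30 days allowed: 0% lost. Only if onsets up to 30 days after end of study are also recorded does a loss appear, about 1.9% with onset uniform over Days 0-180.

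**3. Year only, completer.** The imputed date is 1 July of the onset year.

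- Consent 2 January to 1 July (181 dates): 1 July lies between consent and Day 180, so the event is kept.
- Consent 2 July to 31 December (183 dates): 1 July of the same year precedes consent, and 1 July of the next year is past Day 180, so the event is dropped.
- Consent 1 January: 1 July is Day 181, so the event is dropped.

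Dropped: 184 / 365 = 50.4%. With onset uniform over Days 0-150 this splits into 29.6% before consent and 20.8% past the window; over Days 0-120, 33.7% and 16.7%. The ± 3 days allowed for the Day 150 contact shift the boundary by up to three consent dates.

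**4. Year only, termination at Day 60.** The window closes at Day 90, so only the 91 consent dates from 2 April to 1 July keep the event. Dropped: 274 / 365 = 75.1%. Example: consent 5 January, termination 6 March, window closes 5 April, imputed 1 July.

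**5. Medication stopped 1-30 days before Day 0, day missing.** With a stop on day k of the month and d days before Day 0, the imputed stop lies more than 30 days before Day 0 when k + d > 45. For each k from 16 upward that is k − 15 values of d, which again total 1,523 over the year. Lost from the look-back: 1,523 / (365 × 30) = 13.9%.

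**The case against.** The strongest answer is that the rule was never meant for adverse events. The one date Section 7.3 names for imputation is the diagnosis date, which feeds a single baseline summary. On that reading the rule does nothing to the safety tables. Section 10.1 speaks of when events occurred and does not tell anyone to exclude on an imputed date. Adverse events are assessed at contacts about 30 days apart (Section 3.0), so an on-study event known only by its year may be rare or absent. Data outside the mock-up tables go to listings (Section 8.0), and serious events receive narratives (Section 10.1).

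Much of this stands. It makes the loss conditional and probably small. It does not settle the wording: the rule's subject is dates in general, the following sentence does not say that only the diagnosis date is covered, and listings and narratives do not repair table counts.

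Three stronger readings are tempting and are not supported:

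- *Adverse-event counts are biased downward.* The SAP nowhere says that onset dates are imputed, so this holds only if the rule is applied to them.
- *If the rule covers only the diagnosis date, partly dated events cannot be placed at all.* A known month lying wholly between consent and end of study + 30 days needs no imputation. Only boundary months and missing months are uncertain.
- *Prior testosterone could be misclassified as used on study.* Section 11.5 tabulates the look-back and the study period as one set, with no prior versus on-study split. A stop date moved to on or after Day 0 leaves the medication in the same table. Only the loss from the look-back matters.

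**Conclusion.** The concern holds as a minor wording defect with a conditional effect. If the rule is applied as worded to onset dates, about 13% of day-missing events with onset in Days 0-30 would be dropped and about 3% over Days 0-150, all of them in the consent month of patients consenting on the 16th or later. None would move past the window if onset is by end of study. About half of year-only events would be dropped for a window to Day 180, and more after early termination.

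These figures rest on evenly spread consent and uniform onset, and they apply only to partly dated events. The SAP does not say how many there are, so the total effect cannot be computed and may be close to nil. If the rule is confined to the diagnosis date, it has no effect on the safety tables.

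**What to change.** In Section 7.3, state that the 15th / 1 July rule applies only to the date of hypogonadism diagnosis and that the imputed date may not be later than Day 0.

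In Section 10.1, state that a partly dated adverse event stays in the tables unless its known date parts or its stop date place it outside the window.

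In Section 11.5, state that a partly dated medication stays in the table unless its known date parts place it wholly before the 30-day look-back.

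The cost is two or three sentences and a small programming change. The downside is that a few events or medications from before their window may be counted, which for safety data is the cautious direction.

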5.0 ANALYSIS ENDPOINTS

5.1 Primary Efficacy Endpoints

Primary efficacy is the self-reported patient satisfaction with treatment assessed by the Treatment Satisfaction Questionnaire for Medication (TSQM), a validated, 9-item instrument with domains for Effectiveness, Convenience and Global Satisfaction.

The primary efficacy endpoints are:

- change in satisfaction for each TSQM domain from Visit 1 (Day 0) to Visit 4 (Day 90) for non-naïve BID patients
- change in satisfaction for each TSQM domain from Visit 1 (Day 0) to Visit 5 (Day 120) for non-naïve TID patients

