9.0 EFFICACY ANALYSES

9.1 Primary Efficacy Analyses

The primary efficacy analyses will be performed using the ITT and the respective PP populations.

BID Treatment Group:

TSQM domain scores at Visit 1, Visit 2, Visit 3 and Visit 4 will be summarized and presented descriptively for non-naïve patients. There are three domains which include effectiveness (3 items), convenience (3 items) and global satisfaction (3 items).

TSQM domain change from baseline (Visit 1) scores at Visit 2, Visit 3 and Visit 4 (primary endpoint) will be summarized and presented descriptively for non-naïve patients using 2 different approaches, LOCF and no LOCF. Change from baseline scores will be analysed using a two-sided paired t-test or a non-parametric equivalent if warranted by the data.

TID Treatment Group:

TSQM domain scores at Visit 1, Visit 2, Visit 3, Visit 4 and Visit 5 will be summarized and presented descriptively for non-naïve patients. There are three domains which include effectiveness (3 items), convenience (3 items) and global satisfaction (3 items).

TSQM domain change from baseline (Visit 1) scores at Visit 2, Visit 3, Visit 4 and Visit 5 (primary endpoint) will be summarized and presented descriptively for non-naïve patients using 2 different approaches, LOCF and no LOCF. Change from baseline scores will be analysed using a two-sided paired t-test or a non-parametric equivalent if warranted by the data.

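### The Day 30 score that SAP section 7.3 requires for changes from Day 0 removes patients whose Day 0 and endpoint scores were both observed, at least from the LOCF change

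*SAP*

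**What the plan says.** Section 5.1 defines the primary endpoint by two scores. For BID it is "change in satisfaction for each TSQM domain from Visit 1 (Day 0) to Visit 4 (Day 90) for non-naïve BID patients"; for TID it is "change in satisfaction for each TSQM domain from Visit 1 (Day 0) to Visit 5 (Day 120) for non-naïve TID patients". Day 30 plays no part in either.

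Section 7.3 allows LOCF only when a Visit 2 score exists, and explains this as ensuring enough exposure for a change to be measurable. For qADAM the wording is "For LOCF to apply there must be at least a Visit 2 question available". It then sets a condition for entering the paired-change output. For TSQM, changes from Day 0 "will require both TSQM domain scores at Visit 1/Day 0 and Visit 2/Day 30 to be available to be included in output". For qADAM they "will require both total qADAM scores at Visit 1/Day 0 and Visit 2/Day 30 to be available". The TSQM paragraph goes on: "Summaries for paired change from Visit 2/Day 30 will require the TSQM domain scores at Visit 2/Day 30 to be available".

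Section 9.1 presents the change "using 2 different approaches, LOCF and no LOCF", in the ITT and the respective PP populations. Sections 6.2 and 6.3 admit a dosed patient to ITT on a post-dose measurement at any one of the listed visits. Sections 6.6 and 6.7 ask for completion without major deviations and name no Day 30 score.

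**The concern.** The Day 30 contact is a telephone visit. The endpoint visit, at Day 90 or Day 120, is a clinic visit. A patient who misses the call but attends the clinic supplies everything that section 5.1 asks for, yet section 7.3 excludes that patient's change. The primary summary would then depend on whether an intermediate questionnaire was completed, which is not part of the endpoint.

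What is at stake is the loss of observed primary-endpoint data from at least one of the two planned presentations, and a selection effect if patients who miss Day 30 differ in satisfaction from those who do not. The same applies to the qADAM changes from Day 0 among the secondary endpoints.

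**Working it through.** The SAP has no figure to reproduce here: section 4.0 plans about 100 participants without a formal calculation. The main check is logical.

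**Step 1: patterns.** Take a dosed non-naïve BID patient with Visit 1 and Visit 4 observed, and apply sections 6.2 and 7.3.

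| Visit 2 | Visit 3 | In BID ITT (6.2) | In paired change under 7.3 |
|---|---|---|---|
| observed | observed | yes | yes |
| observed | missing | yes | yes |
| missing | observed | yes | no |
| missing | missing | yes | no |

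All four patterns have an observed Day 0 to Day 90 change, and two of the four are excluded. Exclusion depends on Visit 2 alone, so the result is the same for TID with Visit 5 as the endpoint. The excluded patient can also be in PP, unless a missed call counts as a major deviation.

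**Step 2: reach of the rule.** The wording covers paired-change summaries without limit, so taken literally it binds both the LOCF and the no-LOCF outputs. It stands, however, in the LOCF paragraph. The sentence that follows asks for Visit 2 alone for changes from Visit 2, which works only if later visits are filled by LOCF. An LOCF-only reading is therefore plausible. The exclusions in the table hold for the LOCF output under either reading.

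**Step 3: the exposure reason.** A patient scored at Day 90 or Day 120 has been followed for longer than one scored at Day 30. A minimum-exposure requirement is a reason not to carry forward very early values. It gives no ground for dropping a later value that was observed.

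**Step 4: illustration, all inputs assumed.** Let m be the share of patients with Day 0 and endpoint scores but no Day 30 score. Let D be the difference in mean change between patients without and with a Day 30 score, in score points.

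- Patients lost = N × m. With an assumed N = 50, m = 5%, 10% and 20% give 2.5, 5 and 10.
- Standard error ratio = sqrt(1/(1 − m)), with the SD held constant: 1.026, 1.054 and 1.118.
- Distance between the retained mean and the mean of all observed changes = m × D: 0.05 × 5 = 0.25 points; 0.10 × 10 = 1.0 point; 0.20 × 20 = 4.0 points. It is zero if D = 0, and D may have either sign.

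**The case against.** The strongest reply is that the sentence governs only the LOCF output. The no-LOCF analysis would then keep the patient, and the observed data would still be reported. That reading is fair, and it limits the point: a reader might infer that the primary data are discarded altogether, and the SAP does not establish that. It does not remove the point, because the LOCF change still omits a patient who needs no imputation, and the SAP should say which output the rule binds.

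The rule also has a practical attraction: requiring Visits 1 and 2 and filling the rest gives the same patients at every visit in the LOCF table. That is true, but section 7.3 does not give it as the reason, and the primary endpoint is a change at one visit.

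A reader might also say that the rule contradicts the ITT definition. It does not. Sections 6.2 and 6.3 require no baseline score, so any paired change is a subset of ITT. The fault lies in how this subset is chosen.

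Finally, section 8.0 calls the p-values exploratory and unadjusted. A loss of precision therefore matters less here than in a confirmatory trial. The rule nevertheless decides who enters the descriptive means as well. The Table Mock-Up, which is not at hand, may add detail but would not remove the wording of section 7.3.

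**Conclusion.** The point holds. Under either reading, section 7.3 leaves patients with observed Day 0 and endpoint scores out of the LOCF change for TSQM and total qADAM. Under the literal reading it leaves them out of the no-LOCF change too. It should be corrected, though the practical loss may be small.

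The size and direction are unknown. The SAP gives no missed-visit rate and no split by prior treatment or dose group, so the figures above only illustrate assumed rates. Nothing in the SAP supports saying that the rule makes results look better or worse.

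A reader might go further on Early Termination. TSQM and qADAM are collected at that visit, but sections 7.3 and 9.1 to 9.3 give those scores no stated role. One could infer a conflict, or that the TID endpoint is filled with a score taken before any TID use. The text does not support either. Section 7.2 lists Early Termination as a separate time point, section 9 analyses Visits 1 to 5, and section 8.0 sends data outside the Table Mock-Up to listings, so a listing-only reading is coherent. Section 7.1 also ties the TID group to Visit 5/Day 120, which leaves unclear whether a patient who stops earlier belongs to it. It notes too that the last-dose date was not collected, so whether an Early Termination score was given on treatment cannot be checked against that date. This is a request for clarification only.

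**What to change.** Reword section 7.3 and align sections 9.1 to 9.3 with it:

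- **No-LOCF change:** require only the baseline score and the score at the visit summarised.
- **LOCF change from Day 0:** require the Day 0 score. Use the observed score at the visit whenever it exists; otherwise carry forward the last score from the Day 30 visit or a later scheduled visit. For qADAM, do this by question and then form the total. The minimum-exposure intent is kept, since nothing before Day 30 is carried forward.
- **Change from Visit 2:** keep the Visit 2 condition, because Visit 2 is the baseline there.
- **Early Termination:** state whether TSQM and qADAM scores from that visit are only listed or are used in LOCF.

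The ITT definitions need no change. The cost is minor rewording and programming. Patient numbers may then differ between visits, so each summary should show its own number. LOCF remains a single-value imputation, and the no-LOCF change still omits patients with no score at the visit.
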